X. IRB/IEC & INFORMED CONSENT REQUIREMENTS

Investigators are responsible for obtaining approval from the appropriate IRB/IEC committee prior to study initiation. A copy of IRB/IEC approval documents should be forwarded to the study manager at Smith & Nephew. The local hospital's IRB/IEC committee should give this approval, or should provide a waiver document for the investigator to use a central IRB/IEC. Typically the IRB/IEC approval consists of the protocol, the informed consent form, recruitment materials, and often the case report forms and associated documentation. A copy of the IRB/IEC approval documentation must be provided to sponsor prior to initiation of site, and receipt of subject study binders.

As institutions vary, so do the requirements regarding medical device studies and the subject informed consent requirements. It is the Investigator's responsibility to ensure that appropriate ethical oversight is obtained. Both the investigator and the Sponsor are responsible for ensuring that the study is conducted in compliance with the approved study protocol, Good Clinical Practice (GCP) guidelines, and all applicable regulatory requirements. The Investigator is required to report withdrawal of IRB approval to Smith & Nephew within five days.

XI. DISCLOSURE OF DATA AND DATA-SECURITY

A. Disclosure

Individual investigators may request summaries of their subject data by contacting the clinical study manager. However, if review of another Investigator's data is requested for comparison purposes, the study manager must have confirmation of the involved Investigator's authorization before release of their data can occur. Entire study summaries can be provided without such authorization(s), but the summary will not be stratified by individual surgeon or obtain surgeon identifiers.

B. Data-Security and Confidentiality

The records of this study will be kept private. In any sort of published report, there will be no identifying information. Records for this study may, however, be reviewed by representatives of the Institutional Review Board, which is the committee that oversees research, the United States Food and Drug Administration or other government agencies, and authorized representatives of the Sponsor or Investigator participating in this study may inspect and photocopy all medical records applicable to involvement in this study. To that extent, confidentiality is not absolute.

Surgeons will notify subjects as to any new information during the course of the study which may affect continued participation.

Participating subjects will be asked to sign a consent form. It allows the study Sponsor and the study investigator to collect, process and pass on to the Sponsor organizations any relevant personal de-identified health information collected from the subject, including billing records, during the study. These are activities routinely carried out during all clinical studies. If the subject decides to take part in the study, and the Investigator cannot locate the subject, the site will attempt to make contact using all reasonable methods including use of Private Investigative services. The Private Investigator would only be given subject name, address, phone number, and date of birth as a means of location.

De-identified personal information (including sensitive personal health information, such as medical history and racial / ethnic origin if relevant to the study) will be reviewed, collected on a computer database, stored in electronic or manual files, audited, and / or otherwise processed by:

- the clinical study investigator and his associates
- the study sponsor, Smith & Nephew, and / or its associate companies
- regulatory or other governmental authorities of the United States and other countries
- other persons authorized by the study sponsor
- the investigator's employees
- Other persons or agencies as required by law or allowed by federal regulations

Personal data will be collected and processed to:

- check suitability to take part in the study
- monitor treatment with the study device
- compare and pool treatment results with those of other subjects in clinical studies
- support the development of the study device

- support the licensing application for regulatory approval of the study device in the world
- support the marketing, distribution, sale and use of the study device anywhere in the world

Personal information may be processed within the US or elsewhere in the world. The Sponsor, an associated company, or a carefully selected third party organization may transfer, process, store, or review personal information inside, or outside, the US.

Subjects are free to refuse authorization to transfer personal information. If the subject chooses not to agree to this authorization, the subject may be ineligible to participate in the study. If the subject chooses not to sign the authorization, it will not harm relations with the surgeon.

The subject has the right to inspect their medical records at any time. Research records may be unavailable until the conclusion of the study. At that point, it will be made available. The subject may speak with the surgeon in order to access records.

Whenever personal information is processed; it will be kept confidential and secure to the best of the Sponsor and Investigators ability. It will be used only for the purpose for which it was collected.

Retention of Records – The Investigator and Sponsor are required to maintain all study documentation for at least 3-5 years after the conclusion of the study. Thereafter, written permission is required from the study monitor in order to move or destroy any study document. If subjects wish to revoke authorization to use personal information, the subject shall inform their surgeon in writing. Also, even after participation in the study ends, the Investigators and Sponsor may continue to use and disclose the de-identified health information obtained during the study, before the end of study participation.

C. Use of Information and Publication

Should the investigator wish to publish the results of this clinical investigation or the results of the activities in this clinical trial, the manuscript shall be submitted to Smith & Nephew for review prior to submitting the manuscript for publication.

D. Subject Drop-out/Withdrawal

Subjects may withdraw at any point during the study. A final evaluation will be completed for all subjects who do not finish the study, and the reason for the withdrawal will be documented. After withdrawing from the study, no effort will be made to follow the subject. The Investigator will sign an End of Study/Exit case report form stating the reason the subject withdrew from the study. However, some actively enrolled subjects will not return for follow-up exams due to a variety of reasons.

Often, actively enrolled subjects move during the course of the study without informing the study site. The investigator/study site is committed to use every reasonable measure to obtain follow-up clinical data. The Sponsor reimburses sites for data collection activities associated with subject clinic follow-up. The Sponsor reimburses reasonable examination and x-ray fees if not covered by subject's insurance or are otherwise considered non-standard practice at a clinic or institution. Due to the long length of the study, sites will attempt to contact still active but non-respondent subjects using phone calls, regular mail, e-mail, certified letters or other means to urge subjects to return for clinic follow-up or ascertain if a subject has moved, died, or otherwise become lost to follow-up. These actions, along with any other options available to the site, should be followed to exhaust all reasonable means in locating lost subjects. These actions should be documented in the subject's records and may be performed concurrently or in parallel.

XII. COMPLETION OF STUDY

The Investigator is expected to complete enrollment and follow up per the clinical trial agreement. Continuation of this study beyond the agreement must be mutually agreed upon in writing both by the investigator and by the sponsor. It is agreed that either the investigator or the sponsor, may terminate this study before the above date, provided a written notice is submitted at a reasonable time in advance of intended termination. After conclusion of the study, the sponsor will prepare a clinical summary which will include tabulations of the data used to evaluate safety and efficacy.

XIII. INVESTIGATOR AGREEMENT

A fully-executed Statement of Investigator that includes the investigator and co-investigators, must be in place prior to any study-related activities occurring.

XIV. REFERENCES

1. Hart, JA. Joint replacement surgery. *Med J Aust.* 180: S27-30, 2004.
2. Brooks, PM, and JA Hart. The bone and joint decade: 2000-2010 {Editorial}. *Med J Aust.* 172:307-308, 2000.
4. David Collett. "Modelling Survival Data in Medical Research"Chapman&Hall/CRC . Second Edition. Pg.151-153

1 LIST OF ABBREVIATIONS

Abbreviation	Definition
ADE	Adverse Device Effect
AE	Adverse Event
BMI	Body Mass Index
CRF	Case Report Form
DevD	Device Deficiency
ISO	International Organization for Standardizations
KOOS	Knee Disability and Osteoarthritic Outcome Score
KSS	Knee Society Score
N (or n)	Total Sample Size (or subgroup sample size)
QoL	Quality of Life
S+N	Smith & Nephew Inc.,/T. J. Smith & Nephew Ltd./Smith+Nephew Orthopedics
SADE	Serious Adverse Device Effect
SAE	Serious Adverse Event
SAP	Statistical Analysis Plan
SAF	Safety Population
TFL	Table, Figure and Listing
TKS	Total knee System
UADE	Unanticipated Adverse Device Effect
USADE	Unanticipated Serious Adverse Device Effect

CONFIDENTIAL AND PROPRIETARY

This document contains information that is confidential and proprietary to Smith & Nephew PLC and Smith & Nephew, Inc. and is intended for use only by Smith+Nephew and its manufacturer. It shall not be reproduced or copied in whole or in part, nor shall the contents be disclosed by any means without prior written permission from Smith+Nephew, nor shall anyone make any use of it that is contrary to the expressed or implied wishes of Smith+Nephew.

Statistical Analysis Plan

A Prospective, Multi-Center, Non-Randomized, Safety and Efficacy Clinical Study of the LEGION™ Primary Knee System for Primary Total Knee Replacement in Subjects with Degenerative Knee Disease

Number: 10-4042
ST: 1113
Version: Final 1.0, 15-Feb-2021
Page: 5 of 18

2 INTRODUCTION

This statistical analysis plan (SAP) is written to specify the details of the statistical analyses for the Legion Primary Total Knee System (TKS) study with protocol ID: 10-4042. This SAP composition is based on version 3.0 of the protocol dated 01 February 2011 and its accompanying case report forms (CRFs). The contents of this SAP and of its accompanying shell mockups will serve as guideline for the programming of all tables, figures and listings (TFLs) that would summarize the data.

3 STUDY DESIGN

This is a prospective, consecutive series, multi-center clinical study of the LEGION™ TKS. The study design will facilitate the assessment of the safety and effectiveness profiles of the LEGION™ TKS in subjects with degenerative knee disease requiring primary total knee replacement.

Subjects who consent to participate in this study and who satisfy the study's inclusion will be enrolled. Up to 138 subjects will be enrolled at a maximum of 8 investigational sites, with an expectation of 18 subjects (up to a maximum of 28 subjects) enrolled at each site. Table 1 displays the study's schedule of events.

Table 1. Schedule of events

Study Activity	Preop	O/D	3 mo (± 2)	1 yr (± 3 mo)	2 yr (± 6 mo)	3 yr (± 1 yr)	5 yr (± 1 yr)	7 yr (± 1 yr)	10 yr (± 1 yr)
Inclusion/exclusion Form	X	-	-	-	-	-	-	-	-
Informed Consent	X	-	-	-	-	-	-	-	-

CONFIDENTIAL AND PROPRIETARY

This document contains information that is confidential and proprietary to Smith & Nephew PLC and Smith & Nephew, Inc. and is intended for use only by Smith+Nephew and its manufacturer. It shall not be reproduced or copied in whole or in part, nor shall the contents be disclosed by any means without prior written permission from Smith+Nephew, nor shall anyone make any use of it that is contrary to the expressed or implied wishes of Smith+Nephew.

Statistical Analysis Plan

A Prospective, Multi-Center, Non-Randomized, Safety and Efficacy Clinical Study of the LEGION™ Primary Knee System for Primary Total Knee Replacement in Subjects with Degenerative Knee Disease

Number: 10-4042
ST: 1113
Version: Final 1.0, 15-Feb-2021
Page: 6 of 18

Demographics/ Med History Form	X	-	-	-	-	-	-	-	-
Clinical KSS/KOOS	X	-	X	X	X	X	X	X	X
Operative/Discharge Form	-	X	-	-	-	-	-	-	-
Radiograph Analysis	-	X	X	X	X	X	X	X	X
Adverse Event Form	-	†	†	†	†	†	†	†	†
End of Study/Exit Form	-	-	†	†	†	†	†	†	†

† This form should be completed when necessary.

4 STUDY OBJECTIVES

The objective of this study is to establish the safety and efficacy of the LEGION™ Primary Total Knee System at each postoperative time point.

5 STUDY ENDPOINTS

5.1 Primary Endpoint

- Cumulative percent survival.

5.2 Secondary Endpoints

- Surgical and device related adverse events,
- Knee Society Score (KSS),
- Knee Osteoarthritis Outcome Score (KOOS) and
- Radiographic evaluation.

5.3 Exploratory Endpoints

Not applicable.

CONFIDENTIAL AND PROPRIETARY

This document contains information that is confidential and proprietary to Smith & Nephew PLC and Smith & Nephew, Inc. and is intended for use only by Smith+Nephew and its manufacturer. It shall not be reproduced or copied in whole or in part, nor shall the contents be disclosed by any means without prior written permission from Smith+Nephew, nor shall anyone make any use of it that is contrary to the expressed or implied wishes of Smith+Nephew.

Statistical Analysis Plan

A Prospective, Multi-Center, Non-Randomized, Safety and Efficacy Clinical Study of the LEGION™ Primary Knee System for Primary Total Knee Replacement in Subjects with Degenerative Knee Disease

Number: 10-4042
ST: 1113
Version: Final 1.0, 15-Feb-2021
Page: 7 of 18

5.4 Safety Endpoints

- Overall summary of AEs,
- Incidence of AEs by severity,
- Incidence of AEs by relationship to study device,
- Incidence of AEs that led to discontinuation,
- Incidence of AEs by outcome,
- Incidence of serious adverse events (SAEs) by relationship to study device,
- Incidence of adverse device effects (ADEs)
- Incidence of serious adverse device effects (SADE)
- Incidence of unanticipated serious adverse effects (USADEs), and
- Incidence of unanticipated adverse device effects (UADEs) and.
- International Organization for Standardizations (ISO) AEs

6 STATISTICAL CONSIDERATIONS

6.1 Determination of Sample Size

The sample size estimate for this study was calculated to determine the non-inferiority of the study device to a literature-specified reference proportion using a non-inferiority margin, $\delta > 0$.

Based on this, the following hypotheses was postulated:

$$H_0 \text{ (null): } \pi_0 - \pi \geq \delta$$

$$H_a \text{ (alternate): } \pi_0 - \pi < \delta$$

where π is the cumulative percent survival of study device, π_0 is the literature-specified reference percent survival and $\delta = 0.07$.

With an α (Type I error) = 0.05 and power, Type II error, $\beta = 0.2$ i.e. Statistical Power = 80%, sample size, n was calculated using the following formula (Chow et al, 2003):

CONFIDENTIAL AND PROPRIETARY

This document contains information that is confidential and proprietary to Smith & Nephew PLC and Smith & Nephew, Inc. and is intended for use only by Smith+Nephew and its manufacturer. It shall not be reproduced or copied in whole or in part, nor shall the contents be disclosed by any means without prior written permission from Smith+Nephew, nor shall anyone make any use of it that is contrary to the expressed or implied wishes of Smith+Nephew.

Statistical Analysis Plan

A Prospective, Multi-Center, Non-Randomized, Safety and Efficacy Clinical Study of the LEGION™ Primary Knee System for Primary Total Knee Replacement in Subjects with Degenerative Knee Disease

Number: 10-4042
ST: 1113
Version: Final 1.0, 15-Feb-2021
Page: 8 of 18

$$n = \frac{(z_\alpha + z_\beta)^2 [\pi(1 - \pi)]}{(\pi - \pi_0 - \delta)^2}$$

The cumulative percent survival for the study device is unknown for this population, but there is no reason to believe that it would be less than the reference rate. Therefore, a conservative success rate of 93.1% for the study device was assumed at 10 years. Thus, 96 subjects will be required to detect non-inferiority of the study device. Assuming further that 30% of subjects enrolled will be lost to follow up by the end of 10 years, a sample size of at least 138 subjects was to be enrolled in this study.

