For the current study, the revision free rate will be based on knowledge of parametric proportional hazards models. The survival times with an exponential distribution have a constant hazard function associated with exponential distributed survival time. Thus, for individuals sampled from this exponential survival distribution, the probability of surviving beyond time $t=8$ years is 0.95. The entire survival distribution can be defined by the same parameter value $\lambda=0.0064$ (nQuery Advisor 6.01).

B. Non-inferiority Analysis

As previously reported, an annual survival rate was extrapolated using equivalency of exponentially distributed survival times to determine 10 year survivorship. As such, the current 10-year investigation will utilize a control survival rate of approximately 93.7% (nQuery Advisor 6.01).

All subjects implanted with the LEGION® Primary Knee System, who meet the inclusion and exclusion criteria and who gave their voluntary consent to participate in the study will be included in the analysis. The analysis will include the description of subject demographics and baseline characteristics. Accountability data will include the number of subjects enrolled and the followup data collected. Data will be analyzed separately for changes from preoperative at 3 months, 1 year, 2 years, 3 years, 5 years, 7 years, and 10 years(if required). Safety will be assessed by identifying and summarizing device-related adverse events throughout the study.

The sample size is calculated based on the non-inferiority of the study device; the following hypotheses will be tested to test the difference in cumulative percent survival of the study device with the literature reference rate with a non-inferiority margin, $\delta>0$:

$$H_0: \pi_0 - \pi \geq \delta$$

$$H_a: \pi_0 - \pi < \delta$$

Where π is the cumulative percent survival of study device and π_0 is the reference rate, respectively. $\delta=0.07$. For these hypotheses, rejection of the null hypotheses will imply non-inferiority of the study device compared to the reference rate.

For the above hypotheses, the sample size for a specified α and power $100(1 - \beta)\%$ is given by,

$$n = \frac{(z_\alpha + z_\beta)^2 [\pi (1 - \pi)]}{(\pi_0 - \pi - \delta)^2}$$

(Chow et al, 2003), where δ is the non-inferiority margin and nonnegative number.

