The cumulative percent survival for the study device is unknown for this population, but there is no reason to believe that it would be less than the reference rate. Therefore, a conservative success rate of 93.1% for the study device is used at 10 years. The non-inferiority margin δ of 0.07 is chosen in the study (p13, Chow, Shao, and Wang, 2003). 96 subjects are required to achieve $100(1 - \beta)\% = 80\%$ power to detect non-inferiority at the Significance level of $\alpha = 0.05$. Based on the experience study, allowing 30% of the subjects lost to follow up by the end of 10 years, a sample size of at least 138 subjects are needed in this study. Therefore, a total of 138 subjects will be enrolled into the study in up to 8 clinical sites.

C. Statistical Methods

Primary and secondary outcomes will be evaluated with the use of listings and summary statistics. 95% confidence intervals will be calculated for proportions and averages corresponding to the clinically significant outcomes. Improvement in pain and function will be analyzed using t-test or Wilcoxon Rank tests. Kaplan-Meier estimates will be used to analyze the survivorship of the prosthesis. For survivorship analyses, revision will be defined as failure. Adjustment of prognostic factors to the improvement in outcomes will be performed if needed using appropriate parametric or non-parametric statistical analysis. All statistical analyses and calculation of confidence intervals will be performed using SAS or other appropriate statistical software. An alpha value of $\alpha=0.05$ will be used in all hypothesis testing.

Experience from numerous studies has revealed that most of the missing data are usually due to lost to follow-up, revision, death and subject withdrawal. A complete accountability along with the explanation for lost-to-follow-up, death, revision, and withdrawn subjects will be provided in the final study report. The missing due to revision will be treated as device failure. A complete assessment of the informative/non-informative missing data will be performed using Kaplan-Meier (KM) method. The KM estimate of the success rate along with the 95% confidence interval of the estimate will be included in the final report.

IX. STUDY SUPERVISION

A. Investigator Responsibilities

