7 STATISTICAL ANALYSIS

7.1 General

Smith+Nephew's Global Biostatistics group will conduct the statistical analysis for this study. Unless otherwise stated, significance tests and hypothesis testing will be two-sided, performed at the 5% significance level. Resulting p-values will be quoted and 95% two-sided confidence intervals will be generated where appropriate. All p-values will be rounded to three decimal places, p-values less than 0.001 will be presented as '<0.001' in all tables.

CONFIDENTIAL AND PROPRIETARY

This document contains information that is confidential and proprietary to Smith & Nephew PLC and Smith & Nephew, Inc. and is intended for use only by Smith+Nephew and its manufacturer. It shall not be reproduced or copied in whole or in part, nor shall the contents be disclosed by any means without prior written permission from Smith+Nephew, nor shall anyone make any use of it that is contrary to the expressed or implied wishes of Smith+Nephew.

Statistical Analysis Plan

A Prospective, Multi-Center, Non-Randomized, Safety and Efficacy Clinical Study of the LEGION™ Primary Knee System for Primary Total Knee Replacement in Subjects with Degenerative Knee Disease

Number: 10-4042
ST: 1113
Version: Final 1.0, 15-Feb-2021
Page: 9 of 18

Where data summaries are specified, categorical and ordinal variables will be summarized with frequencies and percentages. Continuous variables will be summarized with the following summary statistics: number of observations, mean, median, standard deviation, minimum and maximum values.

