7.15 Changes in Analysis Methods Specified in the Protocol

The protocol-specified analysis of the primary endpoint was planned to be inferentially performed using a non-inferiority approach. This study is now being terminated early, thus, the primary endpoint will only be descriptively summarized.

CONFIDENTIAL AND PROPRIETARY

This document contains information that is confidential and proprietary to Smith & Nephew PLC and Smith & Nephew, Inc. and is intended for use only by Smith+Nephew and its manufacturer. It shall not be reproduced or copied in whole or in part, nor shall the contents be disclosed by any means without prior written permission from Smith+Nephew, nor shall anyone make any use of it that is contrary to the expressed or implied wishes of Smith+Nephew.

Smith+Nephew

Statistical Analysis Plan

A Prospective, Multi-Center, Non-Randomized, Safety and Efficacy Clinical Study of the LEGION™ Primary Knee System for Primary Total Knee Replacement in Subjects with Degenerative Knee Disease

Number: 10-4042
ST: 1113
Version: Final 1.0, 15-Feb-2021
Page: 18 of 18

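### Does the sample-size formula printed in SAP 6.1, which gives 69 and not the stated 96, call for a change to the plan?

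*SAP*

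**What the plan says.** Protocol VIII.B and SAP 6.1 state the same design. The null hypothesis is π₀ − π ≥ δ and the alternative is π₀ − π < δ, with δ = 0.07, assumed device survival of 93.1% at 10 years, 80% power and 30% loss to follow-up. On the error rate, SAP 6.1 has "With an α (Type I error) = 0.05". Both documents arrive at 96 evaluable and 138 enrolled. In the SAP's words, "Thus, 96 subjects will be required to detect non-inferiority of the study device".

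The formulas differ in one place. The protocol's denominator is (π₀ − π − δ)²; the SAP's is (π − π₀ − δ)². SAP 6.1 does not print a value for π₀.

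The reference comes from the protocol. Section VIII.A takes registry survival of 95% at 8 years, assumes exponential survival and says "The entire survival distribution can be defined by the same parameter value", λ = 0.0064. Section VIII.B then says "the current 10-year investigation will utilize a control survival rate of approximately 93.7" per cent.

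On testing in general, SAP 7.1 says: "Unless otherwise stated, significance tests and hypothesis testing will be two-sided, performed at the 5% significance level". On reporting, Protocol VIII.C says: "The KM estimate of the success rate along with the 95% confidence interval of the estimate will be included in the final report". SAP 7.10 plans two-sided 95% intervals around the Kaplan-Meier estimates. On the primary endpoint, SAP 7.15 says: "This study is now being terminated early, thus, the primary endpoint will only be descriptively summarized".

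**The concern.** A sample-size section should let a reader rebuild its own number, and SAP 6.1 does not. The swap matters algebraically, because δ keeps its sign when π and π₀ change places. The assumed shortfall of the device is then added to the margin when it should be subtracted from it. Taken literally, the formula asks for fewer subjects as the device gets worse, which contradicts the hypotheses printed in the same section.

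Two further points add to the doubt. If the two-sided default in SAP 7.1 applied to the non-inferiority test, 96 would be too few for 80% power. And the reference rate does not quite follow from the protocol's own hazard. Had the study been sized from the wrong formula, or had a confirmatory test still depended on these inputs, the stated power could not be relied on.

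**Working it through.** **Inputs.** π = 0.931, δ = 0.07, α = 0.05, power 80% and loss 30% are in both documents; π₀ = 0.937 is in Protocol VIII.B only. One-sided z_α = 1.6449 and z_β = 0.8416. The numerator is (1.6449 + 0.8416)² × 0.931 × 0.069 = 0.3972.

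**Reproducing the plan's figure.** With the protocol's denominator, (0.937 − 0.931 − 0.07)² = 0.064², so n = 0.3972 / 0.004096 = 96.96. This supports the stated 96. Enrolment is 96 / 0.7 = 137.1, so 138. Strict rounding up would give 97 and 97 / 0.7 = 138.6, so 139, which is one subject more.

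**SAP formula as printed.** (0.931 − 0.937 − 0.07)² = 0.076², so n = 0.3972 / 0.005776 = 68.76, or 69. With a two-sided 5% level it gives 87.3. Neither is 96, so the number in SAP 6.1 did not come from the formula shown there. Entering δ as −0.07 would restore 0.064² and 96.96, but the SAP defines δ > 0, so the printed expression is a slip.

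**Sidedness.** With the protocol's denominator, one-sided 5% gives 96.96 and two-sided 5% gives 123.1. Only the one-sided reading reproduces 96. Power at 96 is Φ(0.064 / √(0.931 × 0.069 / 96) − z), which is 79.7% for z = 1.645 and 69.6% for z = 1.960. This is a binomial approximation with 96 evaluable subjects, not a Kaplan-Meier calculation.

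**Reference rate.** −ln(0.95) / 8 = 0.00641. Then exp(−0.0064 × 10) = 0.9380, and 0.95^(10/8) = 0.9379. Both round to 93.8%; the stated value is approximately 93.7%. With π₀ = 0.938 the denominator is 0.063², n = 100.07 and one-sided power at 96 is 78.5%. The difference is about three subjects, or about one point of power (79.7% to 78.5%).

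**What uses these numbers now.** SAP 7.10 estimates survivorship with intervals and makes no comparison with π₀ or with π₀ − δ = 0.867. SAP 7.15 removes the only test that would have made one. Correcting the denominator, naming the sidedness or moving π₀ by 0.1 point therefore alters no table, estimate or interval.

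**The case for a change.** The best argument for acting is that the SAP is the governing analysis document and a correction costs a few lines. It says n was calculated with a formula that could not have produced it; it omits π₀; and it leaves a two-sided default in SAP 7.1 with no worded exception in 6.1. A reader could still hold the reported 10-year 95% interval against the protocol's 86.7% threshold, unaware that power for that comparison would have been about 70% at 96, not 80%.

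The misprint is real, and that part stands. The rest is weaker. SAP 6.1 retells a past calculation, and the SAP says it is based on protocol version 3.0, which prints the right formula and supplies π₀. The sidedness can be read from the page: a one-directional alternative and z_α, not z_α/2, with α = 0.05. The default in SAP 7.1 yields wherever something else is stated, and a directional alternative can fairly be read as stating it. A reader who uses the 95% interval is applying a stricter criterion than the design did, which does not make a non-inferiority claim easier.

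Changing the reference would do some harm. Putting 93.8% beside 96 and 80% would create a new mismatch, because that reference needs 100 to 101 subjects and gives 78.5% power at 96. It would also move the design threshold from 86.7% to 86.8% after the decision to terminate. Keeping 93.7% as the approximate historical design value is sounder.

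**Conclusion.** No change to the plan follows. The swapped terms in SAP 6.1 are a transcription slip: the printed formula gives 69, the protocol's gives 96.96, and the stated 96 and 138 rest on the latter. The unworded one-sided basis is a gap that the notation fills. The reference differs by 0.1 point in a figure that the protocol calls approximate and that extrapolates two years beyond the last registry value at 8 years.

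This rests on two things. The sample size was fixed under the protocol, which is how the past tense in SAP 6.1 reads, so the slip did not set enrolment. And the primary endpoint stays descriptive, as SAP 7.15 says. If a formal non-inferiority claim were brought back, the sidedness and the reference value would need stating first.

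### The stated 80% power at alpha 0.05 is a large-sample figure the design does not deliver: tests that hold about 5% have roughly 61–78% power

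*SAP*

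**What the plan says.** Both documents size the study for non-inferiority of 10-year implant survival against a fixed reference, with margin 0.07. Protocol VIII.B sets the reference at about 93.7% and says that "a conservative success rate of 93.1% for the study device is used at 10 years". SAP 6.1 repeats the assumed rate and the margin, sets alpha at 0.05 and continues: "Statistical Power = 80%, sample size, n was calculated using the following formula". It then concludes: "Thus, 96 subjects will be required to detect non-inferiority of the study device". Both documents allow for 30% loss by 10 years and arrive at 138 enrolled.

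For the analysis, Protocol VIII.C says "Kaplan-Meier estimates will be used to analyze the survivorship of the prosthesis". SAP 7.10 plans Kaplan-Meier estimates with two-sided 95% confidence intervals and names no transformation for them. SAP 7.1 gives the general rule that "significance tests and hypothesis testing will be two-sided, performed at the 5% significance level". Neither document names a non-inferiority test statistic. SAP 7.15 withdraws the non-inferiority inference because the study is ending early and leaves a descriptive summary.

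**The concern.** The sample-size formula contains a single variance, π(1 − π), evaluated at the assumed device rate of 93.1%. Type I error is defined at the non-inferiority boundary, 93.7% − 7% = 86.7%, where the variance is clearly larger. With many events this choice matters little. Here 96 × 0.069 = 6.6 revisions are expected, and it matters a good deal.

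At stake is the accuracy of the stated operating characteristics. Someone who takes SAP 6.1 at face value will believe the design had an 80% chance of showing non-inferiority at a 5% error rate if the device performed as assumed.

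**Working it through.** **Inputs.** π0 = 0.937 (Protocol VIII.B); π = 0.931, δ = 0.07, α = 0.05, power 80%, 30% loss, 96 evaluable and 138 enrolled (Protocol VIII.B and SAP 6.1). Boundary: 0.937 − 0.07 = 0.867.

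**Reproducing 96 and 138.** With the protocol's formula and a one-sided z of 1.645:

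n = (1.645 + 0.842)² × 0.931 × 0.069 / (0.937 − 0.931 − 0.07)² = 96.96, stated as 96. Then 96/0.7 = 137.1, stated as 138.

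A one-sided 0.025 would give 123, so the figure rests on one-sided 5%. (The denominator as printed in SAP 6.1 has the sign of π0 − π reversed and gives about 69. That is a separate point; the protocol's form is used here.)

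**Variances.** At the assumed rate: 0.931 × 0.069 = 0.0642. At the boundary: 0.867 × 0.133 = 0.1153. Ratio: 1.8.

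**Exact binomial, n = 96 with known 10-year status.** X is the number of revisions; size is taken at revision probability 0.133 and power at 0.069.

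| Rule | Size | Power |
|---|---|---|
| X ≤ 7 (exact one-sided 5%) | 4.9% | 65.7% |
| X ≤ 8 (one-sided Wald) | 9.4% | 78.3% |

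The Wald statistic is 1.76 at 8 revisions and 1.32 at 9, against 1.645, so its cut-off is 8. There is no count between 7 and 8, so no rule based on the count gives 80% power at 5%. Rounding up to n = 97 does not help: 64.6% power at size 4.5%, or 77.4% at 8.8%.

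**Normal approximation with the boundary variance in the α term.** Power at n = 96 is 60.7%. The n for 80% power is [(1.645 × √0.1153 + 0.842 × √0.0642) / 0.064]² = 145.5, i.e. 146 evaluable.

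**Kaplan-Meier, simulated with 138 enrolled.** Assumptions not given in the documents: exponential revision times; 30% loss independent of revision and falling early (years 0–3), spread over 10 years, or late (years 7–10); one knee per subject. Non-inferiority is declared if the lower limit at 10 years exceeds 86.7%.

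| Lower limit | Size | Power, early to late loss |
|---|---|---|
| One-sided 95%, log-log | about 4% | 63–75% |
| One-sided 95%, untransformed | about 8% | 77–85% |
| Two-sided 95%, untransformed | about 5% | 69–78% |
| Two-sided 95%, log-log | about 1.6% | 45–59% |

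Taking the tests with size near 5% (exact, boundary-variance, one-sided log-log, two-sided untransformed), power runs from about 61% to 78%. The two-sided log-log limit is lower still because it uses far less than the 5%.

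**The case against.** **The formula is legitimate.** Using the variance at the alternative is a recognised large-sample Wald form, and the calculation reproduces. This stands. A reader might infer that 96 is an arithmetic error or that the formula is simply wrong; the documents do not support that. The fault is that the approximation is anti-conservative at this sample size and event rate.

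**The inflated error belongs to a test that was not planned.** A reader might infer that the planned analysis carries an error of 8–9%. It does not. That size arises with a one-sided 95% Wald or untransformed limit, whereas SAP 7.10 plans two-sided 95% intervals. The untransformed lower limit of such an interval has size about 5%. This also stands, and it removes any ground for ruling out untransformed limits. It does not rescue the claim, since power with that limit is 69–78%.

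**One power figure would be false precision.** The test statistic, the transformation and the timing of loss are not specified, so a narrow figure such as 66–68% cannot be defended as general. This stands, and it is why a range is given. The closest approach to the stated pair was an arcsine-transformed one-sided 95% limit with late loss: 81% power, but at size 5.9%.

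**Nothing depends on it now.** SAP 7.15 removes the test, SAP 7.10 makes no comparison with 86.7%, and SAP 6.1 is largely a record of how the study was sized. This limits the consequence; it does not make the stated power correct. The SAP also analyses knees and allows for bilateral cases, so figures that assume independent subjects are approximate.

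**Conclusion.** The concern holds in a limited form. On the plan's own inputs, 80% power and 5% error are not obtained together. At n = 96 the exact test falls 14.3 points short (80 − 65.7). Across the tests that hold about 5% the shortfall is about 2 to 19 points (80 − 78 to 80 − 61).

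The exact figures need only the documents' inputs, complete 10-year status for 96 subjects and one independent knee each. The Kaplan-Meier figures also rest on exponential revision times and on assumed loss patterns, so they should be read as ranges.

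A reader might go on to infer that the study needs more subjects or that its reported result would be invalid. Neither follows: the primary analysis is now descriptive, and what is overstated is the design power.

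**What to change.** Leave the sizing calculation in SAP 6.1 as the historical record and add a short qualification, repeated in the report and carried into Protocol VIII.B only if the protocol is amended. For example:

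*The 80% power is a large-sample approximation. With 96 subjects of known 10-year status, an exact one-sided 5% test against 86.7% (7 or fewer revisions) has size 4.9% and power 65.7% at 93.1%. With 138 enrolled and 30% loss, the lower limit of an untransformed two-sided 95% Kaplan-Meier interval has size about 5% and power 69–78%, from early to late loss. Across tests holding about 5%, power is roughly 61–78%.*

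Every power figure should name its test, confidence level and loss-timing assumption. If the 10-year interval is nevertheless compared with 86.7%, state the confidence level and the transformation used. Do not enrol more subjects and do not reinstate a test.

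The cost is a few sentences and a less favourable stated power. Changing the protocol as well would need the mutual agreement described in Protocol VII.B, and possibly ethics approval, so the SAP and the report are the cheaper place.
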